5.3 Dose Expansion Cohorts

Once the RP2D is reached, an additional 15 patients will be treated at this dose. For the expansion cohort, patients will continue to be monitored for occurrence of DLT. Participants who go off-study during the 1st cycle of entinostat will be replaced in the escalation phase. Participants who do not complete the first 2 cycles of combined therapy without experiencing a DLT (as DLT period is defined in the first 2 combined therapy cycles) will also be replaced. To be DLT-evaluable, the patient must complete the first two cycles of combined therapy without experiencing a DLT. Any patient who is dose reduced during the entinostat run-in first cycle due to entinostat-related toxicity will be analyzed on the dose level that corresponds to the reduced dose level delivered during the first cycle of combined therapy.

The following early stopping rule for excess toxicity in the expansion cohort will be used: We will cease enrollment in the expansion phase at the dose determined from dose escalation part of the study if we observe two or more DLTs among the first six evaluable patients enrolled in the expansion cohort. An evaluable patient is any patient who received a study drug. If the true toxicity rate is 50% or greater at the MTD then this rule will stop the trial with probability at least .89. Similarly, if the true toxicity rate is 33% at the MTD then this stopping rule will end the trial with probability .65. In that event, a new expansion cohort will start at the dose level immediately below the dose level that was expanded. If the dose level being expanded is dose level -1, then the study will be terminated.

Monitoring of all safety and toxicity data is done by the Principal Investigator and the Corresponding Organization on a real-time basis as data are entered into Medidata Rave using the Web Reporting Module. All participating sites are expected to notify the Principal Investigator when a DLT has occurred.

5.4 General Concomitant Medication and Supportive Care Guidelines

The patients will receive appropriate standard of care, supportive measures as per the institutional guidelines of each participating institution, including but not limited to blood and platelet transfusions, antibiotics, anti-emetics, etc. Hematopoietic growth factors will not be routinely used.

Because there is a potential for interaction of entinostat with other concomitantly administered drugs, the case report form must capture the concurrent use of all other drugs, over-the-counter medications, or alternative therapies. The Principal Investigator should be alerted if the patient is taking any agent known to affect or with the potential for drug interactions. The study team should check a frequently-updated medical reference for a list of drugs to avoid or minimize use of. [Appendix F](#) (Patient Drug Information Handout and Wallet Card) should be provided to patients if available.

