5.4.1 Pembrolizumab (MK-3475)

5.4.1.1 Pembrolizumab (MK-3475) Concomitant Medication

Medications or vaccinations specifically prohibited in the exclusion criteria are not allowed during the ongoing trial. If there is a clinical indication for one of these or other medications or vaccinations specifically prohibited during the trial, discontinuation from trial therapy or vaccination may be required. The investigator should discuss any questions regarding this with CTEP. The final decision on any supportive therapy or vaccination rests with the investigator and/or the subject's primary physician; however, the decision to continue the subject on trial therapy or vaccination schedule requires the mutual agreement of the Investigator, CTEP, and the patient.

Acceptable Concomitant Medications

All treatments that the investigator considers necessary for a patient's welfare may be administered at the discretion of the investigator in keeping with the community standards of medical care. All concomitant medication will be recorded on the case report form (CRF) including all prescription, over-the-counter (OTC), herbal supplements, and IV medications and fluids. If changes occur during the trial period, documentation of drug dosage, frequency, route, and date may also be included on the CRF.

All concomitant medications received within 28 days before the first dose of trial treatment and 30 days after the last dose of trial treatment should be recorded. Concomitant medications administered after 30 days after the last dose of trial treatment should be recorded for SAEs.

Prohibited Concomitant Medications

Patients are prohibited from receiving the following therapies during the Screening and Treatment Phase (including retreatment for post-complete response relapse) of this trial:

- Anti-cancer systemic chemotherapy or biological therapy.
- Immunotherapy not specified in this protocol.
- Chemotherapy not specified in this protocol.
- Investigational agents other than pembrolizumab (MK-3475).
- Radiation therapy

- Note: Radiation therapy to a symptomatic solitary lesion or to the brain may be allowed after consultation with Sponsor.

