11.2 Response criteria

Myelodysplastic syndrome (MDS)

Responses for MDS patients will be defined as in the modified IWG-2006 criteria ([Appendix A1](#) and [Appendix A1](#)). These response criteria do not apply to AML as these patients are required to be in full remission by eligibility criteria. Only relapse and survival as measured by PFS and overall survival will be measured to assess response for AML patients. The OS and PFS will be measured for both AML and MDS as described in [Appendix A1](#) and [Appendix A2](#).

Duration of response: The duration of overall response is measured from the time measurement criteria are met for CR or PR (whichever is first recorded) until the first date that recurrent or progressive disease is objectively documented (taking as reference for progressive disease the smallest measurements recorded since the treatment started).

Duration of stable disease: Stable disease is measured from the start of the treatment until the criteria for progression are met.

Chronic Myelomonocytic Leukemia (CMML)

The definitions below are consistent with those detailed by Cheson, et al for MDS⁶¹ except that, as discussed earlier, for disease progression based on BM blast percentage, the patient must exceed 10% absolute BM blast percentage in addition to increasing above 50% of BM blast percentage at baseline to count as disease progression.

Complete response is defined by bone marrow showing <5% myeloblasts with normal trilineage maturation without dysplasia. When erythroid precursors constitute <50% of marrow cells, the blast percentage is based on total nucleated cells; otherwise, the blast percentage is based on non-erythroid compartment. Peripheral blood criteria consist of Hemoglobin \geq 11 gm/dl, ANC \geq 1 x 10⁹/L, Platelets \geq 100 x 10⁹/L, absence of peripheral blood blasts, all in the absence of transfusions and growth factors.

Partial response is defined by all of the above criteria with the exception of bone marrow blasts decreasing by >50% from pretreatment levels and/or achievement of a less advanced MDS FAB classification.

Stable Disease is defined by failure to achieve PR but without progression for at least 2 months.

Progression is defined according to initial blast percentages:

For patients with <5% blasts: \geq 50% increase in blasts to >10%

For patients with 5-10% blasts: \geq 50% increase in blasts to >10%

For patients with >10-20% blasts: \geq 50% increase in blasts to >20%

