13.2 Sample Size/Accrual Rate

We expect to accrue 1-2 patients with MDS per month once the study is open.

Currently there is no therapy that has been shown to prolong survival in MDS in the post-DNMTi setting and that the expected best response in patients receiving supportive care only in post-DNMTi setting is negligible (1% or less). It is generally accepted that a $\geq 15\%$ ORR in the post-DNMTi is clinically meaningful and would be worth further evaluation in larger studies.

The total number of patients enrolled in the study will range from 21 to 27. The null hypothesis response rate of 1% (only supportive care) will be rejected if we observe 2 or more favorable responses. These criterion has significance level between .02 and .03 using a one-sided binomial test. This criterion has power between .84 and .93 for testing an alternative response rate of 15% with the combination therapy. Therefore, we will treat a total of 21 patients in the combination arm (6 in the first part of the study and 15 in the second part of the study).

DOMESTIC PLANNED ENROLLMENT REPORT						
Racial Categories	Ethnic Categories				Total	
	Not Hispanic or Latino		Hispanic or Latino			
	Female	Male	Female	Male		
American Indian/ Alaska Native	1	1	1	1	4	
Asian	1	1	0	0	2	
Native Hawaiian or Other Pacific Islander	1	0	0	0	1	
Black or African American	1	1	1	1	4	
White	4	4	1	1	10	
More Than One Race	0	0	0	0		
Total	8	7	3	3	21	

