* Dysplastic changes should consider the normal range of dysplastic changes (modification).

† Modification to IWG response criteria.

‡ In some circumstances, protocol therapy may require the initiation of further treatment (eg, consolidation, maintenance) before the 4-week period. Such patients can be included in the response category into which they fit at the time the therapy is started. Transient cytopenias during repeated chemotherapy courses should not be considered as interrupting durability of response, as long as they recover to the improved counts of the previous course.

**APPENDIX A2 MODIFIED INTERNATIONAL WORKING GROUP (IWG)-2006
RESPONSE CRITERIA FOR HEMATOLOGIC IMPROVEMENT**

Hematologic improvement*	Response criteria (responses must last at least 8 wk)[†]
Erythroid response (pretreatment, < 11 g/dL)	Hgb increase by ≥ 1.5 g/dL Relevant reduction of units of RBC transfusions by an absolute number of at least 4 RBC transfusions/8 wk compared with the pretreatment transfusion number in the previous 8 wk. Only RBC transfusions given for a Hgb of ≤ 9.0 g/dL pretreatment will count in the RBC transfusion response evaluation [†]
Platelet response (pretreatment, $< 100 \times 10^9/L$)	Absolute increase of $\geq 30 \times 10^9/L$ for patients starting with $> 20 \times 10^9/L$ platelets Increase from $< 20 \times 10^9/L$ to $> 20 \times 10^9/L$ and by at least 100% [†]
Neutrophil response (pretreatment, $< 1.0 \times 10^9/L$)	At least 100% increase and an absolute increase $> 0.5 \times 10^9/L$ [†]
Progression or relapse after HI [‡]	At least 1 of the following: At least 50% decrement from maximum response levels in granulocytes or platelets Reduction in Hgb by ≥ 1.5 g/dL Transfusion dependence

Deletions to the IWG response criteria are not shown.

To convert hemoglobin levels from grams per deciliter to grams per liter, multiply grams per deciliter by 10.

Hgb indicates hemoglobin; RBC: red blood cell; HI: hematologic improvement.

* Pretreatment counts averages of at least 2 measurements (not influenced by transfusions) ≥ 1 week apart (modification).

[†] Modification to IWG response criteria.

[‡] In the absence of another explanation, such as acute infection, repeated courses of chemotherapy (modification), gastrointestinal bleeding, hemolysis, and so forth. It is recommended that the 2 kinds of erythroid and platelet responses be reported overall as well as by the individual response pattern.

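### The MDS response criteria do not exclude on-treatment count rises caused by growth factors, so such a rise can be scored as hematologic improvement in an ORR test that rejects at two responses

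*Combined protocol and SAP*

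**What the plan says.** **Supportive care.** Section 5.4 leaves supportive measures, including red-cell and platelet transfusion, to each institution's guidelines and adds: "Hematopoietic growth factors will not be routinely used". Growth factors are not named in the prohibited list of Section 5.4.1.1, which also states: "All treatments that the investigator considers necessary for a patient's welfare may be administered at the discretion of the investigator". Glucocorticoids are on that list, except for suspected immune events or, with approval, physiologic doses.

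**Scoring.** ORR is CR, PR or HI (synopsis; Sections 13.1 and 13.4). Appendix A2 scores HI from a rise in hemoglobin, platelets or neutrophils, or from fewer red-cell transfusions, lasting at least 8 weeks. Its footnote on counts covers baseline only: "Pretreatment counts averages of at least 2 measurements (not influenced by transfusions". The blood thresholds for CR and PR in Appendix A1 carry no transfusion or growth-factor condition. For CMML, Section 11.2 requires the complete-response blood values "all in the absence of transfusions and growth factors".

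**Test.** Section 13.2: "The null hypothesis response rate of 1% (only supportive care) will be rejected if we observe 2 or more favorable responses". It gives this rule a "significance level between .02 and .03 using a one-sided binomial test" and power of .84 to .93 at a 15% response rate, for 21 to 27 patients.

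**The concern.** HI is judged mainly on blood counts, and a growth factor acts directly on those counts. Take a patient who starts an erythropoiesis-stimulating agent or G-CSF during combined therapy. If hemoglobin then rises by 1.5 g/dL, or neutrophils double with an absolute gain above 0.5 × 10⁹/L, for 8 weeks, Appendix A2 scores the patient as HI whatever the cause.

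The appendix is also asymmetric. Its allowance for another explanation is attached to progression or relapse after HI, so a count loss with another cause can be set aside and a count gain cannot. Sections 13.4 and 13.5 add no rule.

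The stake is the reading of the ORR test. With a 1% null and a threshold of two, one or two misattributed responses can decide whether the null is rejected.

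**Working it through.** **1. Inputs.** From Section 13.2: null 1%, alternative 15%, n = 21 to 27, reject at two or more responses, one-sided exact binomial.

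**2. Reproduce the plan's figures.** P(X ≥ 2) = 1 − (1−p)^n − n·p·(1−p)^(n−1).

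- Alpha, n = 21, p = .01: 1 − .8097 − .1718 = .0185
- Alpha, n = 27, p = .01: 1 − .7623 − .2079 = .0297
- Power, n = 21, p = .15: 1 − .0329 − .1221 = .845
- Power, n = 27, p = .15: 1 − .0124 − .0592 = .928

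These agree with the stated ranges.

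**3. Slack in the rule.** Let p be the total rate at which patients on an inactive combination would be scored as responders. The documents give no value above 1%, so every larger p is an assumption.

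| Assumed p | P(X ≥ 2), n = 21 | P(X ≥ 2), n = 27 |
|---|---|---|
| 1% (plan) | .0185 | .0297 |
| 2% | .065 | .101 |
| 3% | .130 | .194 |
| 4% | .204 | .294 |
| 5% | .283 | .394 |
| 6% | .362 | .488 |

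The error rate passes .05 at p of about 1.7% (n = 21) or 1.3% (n = 27). One way to reach about 5%, again assumed: 20% of patients receive a growth factor and 20% of those meet HI because of it, so p = 1 − .99 × (1 − .04) = .0496.

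**4. One misattributed response.** If one patient is already wrongly scored, the chance that at least one other patient responds at the 1% rate is 1 − .99^20 = .18 (n = 21) or 1 − .99^26 = .23 (n = 27).

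**5. The 15% target.** The synopsis and Section 13.1 also set an observed ORR of at least 15% for continuation (the synopsis elsewhere says 20%). Since 3/21 = 14.3% and 4/27 = 14.8% fall short, 15% needs 4/21 (19.0%) or 5/27 (18.5%). At p = 4% to 6%, P(X ≥ 4) is .009 to .034 for n = 21 and P(X ≥ 5) is .004 to .021 for n = 27.

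**6. Which routes are open.**

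- *Growth factor to HI:* open for the hemoglobin and neutrophil criteria.
- *Transfusion to HI:* weaker. The rise must last 8 weeks, the alternative erythroid criterion requires at least 4 fewer transfusions per 8 weeks, and transfusion dependence counts as relapse after HI. The hemoglobin-rise and platelet-rise criteria still carry no on-treatment transfusion condition.
- *CR and PR:* Appendix A1 also requires marrow criteria, which count support alone does not meet.
- *Steroids:* narrow, because use is limited as described above.

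**The case against.** The strongest case against has four parts.

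- **The null is already a supportive-care rate.** Section 13.2 says "the expected best response in patients receiving supportive care only in post-DNMTi setting is negligible (1% or less". On its face, responses under supportive care belong to the 1%, and adding to it presumes that they do not. This stands as a limit on the size: the plan neither says whether that figure allows growth factors nor ties it to these criteria, so the higher rates above are illustrations.
- **Two responses do not meet the continuation target.** They are 9.5% of 21 or 7.4% of 27, below 15%, and step 5 shows the target is hard to reach by artefact. This also stands. ORR is a secondary endpoint giving a preliminary estimate. The exposed part is the hypothesis test.
- **An HI-only signal would be visible.** Section 13.4 reports CR, PR and HI rates separately with exact 95% intervals, and concomitant drugs go on the CRF. That helps a reader, but no rule links the recorded drugs to the scoring.
- **The CMML clause is not a ready-made HI rule.** Correct: that section defines no HI category. It shows that the authors applied the condition in one disease group, and no more.

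A reader might go further and infer that growth factors, transfusions and steroids are all freely permitted, and that supportive care will supply the two responses and so declare the combination active. The documents do not support that. Glucocorticoids are prohibited with limited exceptions, transfusion largely works against a sustained HI, growth factors are discouraged, and nothing shows that two such responses would occur.

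**Conclusion.** The gap is real and specific: in MDS patients, a growth-factor-driven rise meeting Appendix A2 for 8 weeks is scored as a response and enters the ORR test. Transfusion is a secondary route. The plan's alpha and power are correct at its own 1%, but a background rate of only 2% would take alpha to .065 (n = 21) or .101 (n = 27), and 5% would take it to .28 or .39. Those rates are assumed, and whether the 1% already covers growth-factor use is not stated. This should be fixed. It does not touch the primary MTD endpoint, and it does not show that a positive ORR result would be false.

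**What to change.** In Appendices A1/A2 and Section 13.4, before responses are reviewed, state that:

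- a lineage count cannot qualify for CR, PR or HI while a growth factor active on that lineage is being given, or within a prespecified window afterwards;
- hemoglobin and platelet values within a prespecified window after transfusion cannot qualify;
- neutrophil HI cannot qualify during systemic steroids, where a steroid-treated patient remains assessable.

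Report ORR with and without the excluded HI. State whether the 1% null allows for growth-factor use.

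Make growth-factor, transfusion and steroid dates mandatory on the CRF; Section 5.4.1.1 makes the recording of dates optional when medication changes.

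Separately, Section 5.4.1.1 (steroids allowed for suspected immune events), Section 5.5 (need for systemic steroids listed among the reasons to end therapy) and Sections 6.2.2 and 6.2.3 (steroids given, with pembrolizumab resumed after taper or stopped if the dose cannot be reduced) must be reconciled on whether such a patient stays on therapy. The third scoring clause depends on the answer.

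**Cost:** a short scoring clause, chosen windows and some required CRF fields. An occasional genuine HI in a supported patient will be lost, and ORR may be slightly lower. Sample size, decision rule and permission to give supportive care are unchanged; with the null held at 1%, alpha and power stay as in step 2. Added after responses are known, with two events deciding the test, the clause would be a post hoc choice.

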5.4.1 Pembrolizumab (MK-3475)

5.4.1.1 Pembrolizumab (MK-3475) Concomitant Medication

Medications or vaccinations specifically prohibited in the exclusion criteria are not allowed during the ongoing trial. If there is a clinical indication for one of these or other medications or vaccinations specifically prohibited during the trial, discontinuation from trial therapy or vaccination may be required. The investigator should discuss any questions regarding this with CTEP. The final decision on any supportive therapy or vaccination rests with the investigator and/or the subject's primary physician; however, the decision to continue the subject on trial therapy or vaccination schedule requires the mutual agreement of the Investigator, CTEP, and the patient.

Acceptable Concomitant Medications

All treatments that the investigator considers necessary for a patient's welfare may be administered at the discretion of the investigator in keeping with the community standards of medical care. All concomitant medication will be recorded on the case report form (CRF) including all prescription, over-the-counter (OTC), herbal supplements, and IV medications and fluids. If changes occur during the trial period, documentation of drug dosage, frequency, route, and date may also be included on the CRF.

All concomitant medications received within 28 days before the first dose of trial treatment and 30 days after the last dose of trial treatment should be recorded. Concomitant medications administered after 30 days after the last dose of trial treatment should be recorded for SAEs.

Prohibited Concomitant Medications

Patients are prohibited from receiving the following therapies during the Screening and Treatment Phase (including retreatment for post-complete response relapse) of this trial:

- Anti-cancer systemic chemotherapy or biological therapy.
- Immunotherapy not specified in this protocol.
- Chemotherapy not specified in this protocol.
- Investigational agents other than pembrolizumab (MK-3475).
- Radiation therapy

- Note: Radiation therapy to a symptomatic solitary lesion or to the brain may be allowed after consultation with Sponsor.
- Live vaccines within 30 days prior to the first dose of trial treatment and while participating in the trial. Examples of live vaccines include, but are not limited to, the following: measles, mumps, rubella, chicken pox, yellow fever, rabies, BCG, and typhoid (oral) vaccine. Seasonal influenza vaccines for injection are generally killed virus vaccines and are allowed; however, intranasal influenza vaccines (e.g. Flu-Mist®) are live attenuated vaccines, and are not allowed.
- Glucocorticoids for any purpose other than to modulate symptoms from an event of suspected immunologic etiology. The use of physiologic doses of corticosteroids may be approved after consultation with the Sponsor.

Patients who, in the assessment by the investigator, require the use of any of the aforementioned treatments for clinical management should be removed from the trial. Patients may receive other medications that the investigator deems to be medically necessary.

The Exclusion Criteria describes other medications which are prohibited in this trial.

There are no prohibited therapies during the Post-Treatment Follow-up Phase.

Co-administration of drugs sensitive substrates of CYPs 1A2, 2B6, 2C8, 2C9, 2C19, and 2D6 with a narrow therapeutic window are permitted, as it appears that entinostat is unlikely to inhibit these enzymes in humans.

5.5 Duration of Therapy

In the absence of treatment delays due to adverse event(s), treatment may continue for one year (maximum 18 cycles or entinostat and maximum 17 cycles of pembrolizumab (MK-3475)) or until one of the following criteria applies:

- Disease progression as defined in modified IWG-2006 ([Appendix A1](#), [Appendix A2](#)) for MDS
- If disease has shown evidence of progression based on an increase in the blast counts according to the modified IWG-2006, but the patient is otherwise clinically stable and his transfusion requirement have not changed, the investigator can give two additional cycles of combined treatment and bone marrow biopsy will be repeated after that cycle. If repeat bone marrow biopsy confirms disease progression, the patient will be taken off the trial.
- Intercurrent illness that prevents further administration of treatment
- Patient decides to withdraw from the study
- General or specific changes in the patient's condition render the patient unacceptable for further treatment in the judgment of the investigator

- Clinical progression
- Patient non-compliance
- Pregnancy
 - All women of child bearing potential should be instructed to contact the investigator immediately if they suspect they might be pregnant (e.g., missed or late menstrual period) at any time during study participation.
 - The investigator must immediately notify CTEP in the event of a confirmed pregnancy in a patient participating in the study.
- Termination of the study by sponsor
- The drug manufacturer can no longer provide the study agent
- Unacceptable adverse event(s), including:
 - Any Grade 2 drug-related uveitis or eye pain or blurred vision that does not respond to topical therapy and does not improve to Grade 1 severity within the re-treatment period OR requires systemic treatment.
 - Grade 3 drug-related autoimmune or inflammatory event including uveitis, pneumonitis, diarrhea, colitis, neurologic adverse events, hypersensitivity reaction, or infusion reaction of any duration requires discontinuation.
 - Any Grade 3 or 4 drug-related laboratory imbalance or electrolyte abnormality, not associated with underlying organ pathology and that do not require treatment except for electrolyte replacements, do not require treatment discontinuation, with the following exceptions with approval of the Principal Investigator:
 - Grade 2-4 hypophysitis or pan-hypopituitarism requires holding pembrolizumab (MK-3475) and discontinuing treatment if unable to reduce corticosteroid dose to ≤ 10 mg of prednisone or equivalent per day within 12 weeks.
 - Grade 4 amylase or lipase abnormalities that are not associated with diabetes mellitus, associated liver or gall bladder inflammation clinical manifestations of pancreatitis and which decrease to <Grade 4 within 1 week of onset may stay on study.
 - Any drug-related liver function test (LFT) abnormality that meets the following criteria requires discontinuation: Grade 3 AST or ALT ($>5 \times$ ULN) and total bilirubin $>3 \times$ ULN.
 - Grade 3 drug-related thrombocytopenia >7 days or associated with bleeding

requires discontinuation.

- Any patient requiring systemic steroid or other immunosuppressive treatment.
- For patients with skin-only toxicity, when symptoms improve to \leq Grade 1, steroid taper should be started and continued over no less than 4 weeks. Discontinue MK-3475 if unable to reduce corticosteroid dose for irAEs to \leq 10 mg. pembrolizumab (MK-3475) treatment may be restarted and the dose modified as specified in the protocol.
- Patients with peripheral thyroiditis and no other autoimmune/inflammatory event may be restarted after a short course of steroids on a stable replacement regimen.
- Any dosing interruption lasting $>$ 12 weeks with the following exceptions:
 - Dosing interruptions $>$ 12 weeks that occur for non-drug-related reasons may be allowed if approved by the Principal Investigator. Prior to re-initiating treatment in a subject with a dosing interruption lasting $>$ 12 weeks, the Principal Investigator must be consulted.
 - Tumor assessments should continue as per protocol even if dosing is interrupted.

The reason(s) for protocol therapy discontinuation, the reason(s) for study removal, and the corresponding dates must be documented in the Case Report Form (CRF).

